## 370 **9. Adherence and Retention Analyses**

### 371 **9.1 Utility Analysis**

372 The amount of CGM use will be tabulated for each treatment arm, in addition to the amount of  
373 closed loop system use in the CL arm. Summary statistics appropriate to the distribution and  
374 range will be reported for the percentage of time using the CGM over the four month period (as  
375 defined above) for each treatment group. The same will be done for the percentage of time using  
376 the closed loop system in the CL arm. Tabulations of summary statistics will also be performed  
377 for the percentage of time spent using the closed loop system while using the CGM in the CL  
378 arm.

379 The percentage of time spent using the CGM will be calculated by dividing the total number of  
380 CGM readings by the expected number of readings during the four-month period. The  
381 percentage of time using the closed loop system in the CL arm will be calculated by dividing the  
382 total amount of time that temporary basal infusion lasts no more than 30 minutes by the  
383 maximum possible amount of time that the system could have been used. The percentage of time  
384 using the closed loop system while using the CGM (in the CL arm) will then be computed by  
385 dividing the time that the closed loop system was operational by the amount of time that the  
386 CGM was available.

387 If a subject drops out of the study in the middle of a period, then the subject will be counted as  
388 not using the CGM or the closed loop system at all during the remainder of the study. Thus, these  
389 time points will be counted as zero use in the calculation of CGM use and closed loop system  
390 use.

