## 4.2 Closed Loop Insulin Delivery

The development of a closed loop system combines glucose monitoring with computer-based algorithm informed insulin delivery. The vital component of such a system, also known as an artificial pancreas (AP), is a computer-based algorithm. The role of the control algorithm is to translate, in real-time, the information it receives from the CGM and to compute the amount of insulin to be delivered by the pump. The other components include a real-time continuous glucose monitor and an infusion pump to titrate and deliver insulin (9).

Automatic suspension of insulin delivery by the pump when a predefined glucose level is reached (threshold suspend insulin pump therapy) represents the simplest form of closed loop insulin delivery. Such a system (Veo (non-US) or Medtronic 530G (US) insulin pump coupled with Minilink sensor (Medtronic Minimed, Northridge, CA, USA) which stops insulin delivery for up to 2 hours is currently commercially available (40-43). In comparison to threshold suspension, hypoglycaemia-prediction algorithms and automatic pump suspension of predictive log glucose suspension (PLGS) systems enable insulin delivery to be suspended when hypoglycaemia is predicted (44). The predictive low glucose management (PLGM) function of the MiniMed 640G (Medtronic Diabetes, Northridge, CA, USA) insulin pump was introduced into clinical practice in Australia and Europe early 2015. A slightly revised version was recently approved by the FDA in the US for the treatment of people with diabetes sixteen years of age and

older (MiniMed 630G; Medtronic Diabetes, Northridge, CA, USA). Since insulin is not delivered in an automated fashion there is no risk of system-induced hypoglycaemia. The risk of consecutive rebound hyperglycaemia and ketonaemia after a temporary suspension of insulin administration is not negligible (45), but only mild rebound hyperglycaemia and no episodes of diabetic ketoacidosis following threshold suspension activation have been reported (43, 46). While threshold suspend insulin delivery systems and predictive low glucose suspension systems might reduce the risk and severity of hypoglycaemic events, neither system mitigates against higher glycaemic levels.

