## **14.6 Utility Evaluation**

The amount of CGM use will be tabulated for each treatment arm, in addition to the amount of closed loop system use in the CL arm and the extension phase. Summary statistics appropriate to the distribution and range will be reported for the percentage of time using the CGM over the four month period (as defined above) for each treatment group. The same will be done for the percentage of time using the closed loop system in the CL arm and the extension phase. Tabulations of summary statistics will also be performed for the percentage of time spent using the closed loop system while using the CGM in the CL arm and the extension phase.

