86            ○ Emotional Problems Subscale  
87            ○ Conduct Problems Subscale  
88            ○ Hyperactivity Subscale  
89            ○ Peer Problems Subscale  
90            ○ Prosocial Subscale  
91            ○ Total Difficulties Score

92       13) Hypoglycemia Fear Survey  
93            ○ Behavior Subscale  
94            ○ Worry Subscale

95       14) WHO-5

96       15) Epworth Sleepiness Scale

97       16) Pittsburgh Sleep Quality Index  
98            ○ Subjective Sleep Quality Subscale  
99            ○ Sleep Latency Subscale  
100           ○ Sleep Duration Subscale  
101           ○ Habitual Sleep Efficiency Subscale  
102           ○ Sleep Disturbances Subscale  
103           ○ Use of Sleeping Medication Subscale  
104           ○ Daytime Dysfunction Subscale

105       17) Children's Sleep Habit Questionnaire  
106           ○ Bedtime Resistance Subscale  
107           ○ Sleep Onset Delay Subscale  
108           ○ Sleep Duration Subscale  
109           ○ Sleep Anxiety Subscale  
110           ○ Night Waking Subscale  
111           ○ Parasomnias Subscale  
112           ○ Sleep Disordered Breathing Subscale

113                   ○ Daytime Sleepiness Subscale

114   All metrics listed above will be outcomes in the main study. In the extension phase, the same  
115   outcomes will be analyzed, with the exceptions of the Pittsburgh Sleep Quality Index and the  
116   Children's Sleep Habit Questionnaire. The primary outcome in the extension phase will be time  
117   in range calculated over the full 18 months.

118   **4.1 Calculation of CGM Metrics**

119   For the primary outcome and all secondary CGM metrics, a single value will be calculated for  
120   each subject for each period by pooling all CGM readings between the treatment initiation visit  
121   and up to 112 days post-initiation visit or the end of treatment visit, whichever comes first. All  
122   glucose sensor readings will be weighted equally in the pooled percentages regardless of how  
123   they distribute across weeks. Data will not be truncated due to protocol deviations.

124   Baseline CGM metrics will be calculated by pooling all readings up to the last 14 available days  
125   of CGM readings prior to randomization.

126   In the extension phase, CGM metrics will be calculated by pooling all readings inclusively  
127   occurring from the day after the last visit of the main study up until the last visit of the extension  
128   phase.

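### SAP 9.1 does not limit closed loop use while using the CGM to time with CGM data, so the ratio may overstate the labelled percentage and could exceed 100%

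*Combined protocol and SAP*

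**What the plan says.** Protocol 14.6 (Utility Evaluation) asks for three summaries: CGM use, closed loop use, and the "percentage of time spent using the closed loop system while using the CGM in the CL arm and the extension phase". It gives no formula for the third.

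SAP 9.1 (Utility Analysis) gives the formulas, for the closed loop arm only:

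- CGM use is the number of CGM readings over the number expected.
- Overall closed loop use is the "total amount of time that temporary basal infusion lasts no more than 30 minutes by the" longest time for which the system could have run.
- Closed loop use while using the CGM is found by "dividing the time that the closed loop system was operational by the amount of time that the" CGM was available.

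The temporary basal criterion is the only definition of closed loop time in the section. It is a pump-record criterion and does not mention a CGM reading. Neither document limits the numerator of the third measure to CGM time or caps the ratio.

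**The concern.** The label describes a conditional percentage: of the time with CGM data, how much was spent in closed loop. The numerator should then be the overlap of the two. The formula instead takes all closed loop time, whether or not a CGM reading was present. If the pump criterion is met at times when readings are missing, that time counts in the numerator but not in the denominator.

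CGM gaps are foreseen. Protocol 11.1.7 lists sensor detachment, early end of sensor life and intermittent communication failure among the expected problems that will not be recorded as device deficiencies. The conditional percentage is meant to describe system operation apart from sensor wear, so it should not itself move with the number of gaps. At stake are a descriptive percentage that may favour the system and, for some children, a value above 100% that has no meaning.

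**Working it through.** The documents state no value for this measure, so there is no figure to reproduce. The check has two parts: an identity, and an illustration on stated assumptions.

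**Identity.** Let G be the time with CGM available and C the closed loop time by the SAP criterion.

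- As labelled: (C within G) / G.
- As computed: C / G = (C within G) / G + (C outside G) / G.
- Difference: (C outside G) / G. This is never negative, and it is zero if all closed loop time lies within CGM time.
- C / G is above 100% exactly when (C outside G) is longer than (G without C).
- Ceiling: C cannot exceed the whole period, so C / G is at most 1 / availability, for example 1 / 0.90 = 111% or 1 / 0.95 = 105%.

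**Illustration.** SAP 4.1 pools CGM data over at most 112 days, which is 112 × 24 = 2688 h. The following are assumptions, because the documents do not supply them: CGM availability, the number of gaps, and up to 30 minutes of closed loop time counted per gap (capped at total gap time). The 30 minutes is borrowed from the temporary basal criterion. The SAP does not say that it bounds what is counted after CGM loss.

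At 90% availability, G = 0.90 × 2688 = 2419 h and the time without CGM is 269 h.

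| Gaps | Closed loop time outside G | Overstatement |
|---|---|---|
| No time counted in gaps | 0 h | 0 points |
| One every two days | 56 × 0.5 = 28 h | 28 / 2419 = 1.2 points |
| One per day | 112 × 0.5 = 56 h | 56 / 2419 = 2.3 points |
| Two per day | 224 × 0.5 = 112 h | 112 / 2419 = 4.6 points |

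The period length cancels below the cap. At one gap per day the result is simply 0.5 / (24 × 0.90) = 2.3%.

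**Sensitivity to availability.** At 60%, G = 1613 h, and one to two gaps per day give 56 / 1613 = 3.5 to 112 / 1613 = 6.9 points. At 98%, only 53.8 h lie outside G = 2634 h, so the overstatement cannot exceed 53.8 / 2634 = 2.0 points.

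**When 100% is passed.** At 90% availability and one gap per day, the true share must be above 100 − 2.3 = 97.7%. A true 98% would be reported as 100.3%; a true 90% would be reported as 92.3% and would look unremarkable.

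**The case against.** The strongest reply is that the two quantities may coincide in practice. Protocol 4.2 says "The role of the control algorithm is to translate, in real-time, the information it receives from the CGM", so closed loop time should lie largely within CGM time. If it does so entirely, the formula is exact. A programmer could also read the condition in the label into the word operational. The first part stands: it limits the size of the problem and allows zero. It does not repair the definition, because the SAP measures closed loop operation by temporary basal duration and not by whether the algorithm had a reading.

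Three stronger readings are tempting, and the documents do not support them.

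- A reader might infer that the percentage is overstated. That needs evidence that closed loop time is counted without CGM. No section says what the pump does on CGM loss, how long a temporary basal is set to run, or how often gaps occur.
- A reader might infer a large bias from frequent gaps. Four per day at 90% availability would give 224 / 2419 = 9.3 points, but this counts 224 of the 269 h without CGM as closed loop. Nothing in the documents points to that case.
- A reader might infer that the measure hides poor connectivity. CGM use and overall closed loop use are tabulated separately in the same section. Sensor gaps lower the first, and closed loop time lost while CGM is available lowers the second.

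The measure also carries little weight. Protocol 10.5 lists only the closed loop and CGM percentages as utility endpoints, and the per-protocol set in SAP 5.1 uses closed loop use over the closed loop period, not this ratio.

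**Conclusion.** The point holds as a mismatch between a label and its formula. As written, SAP 9.1 does not compute the conditional percentage that it names. Any error is upward, and the ratio is not bounded by 100%. Whether there is an error in the trial data cannot be told from the documents. The plausible size runs from zero to about 5 points, if CGM availability is 90%, at most 30 minutes is counted per gap and there are no more than two gaps per day. Lower availability at the same gap rate would raise it.

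This is a minor point. It affects one descriptive tabulation and no hypothesis test or analysis set. For the extension phase the formula is not specified at all, so the error cannot be said to exist there; the definition is simply open.

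**What to change.** In SAP 9.1, define the numerator of closed loop use while using the CGM as the time that meets the closed loop criterion and also has a CGM reading available, matched on time stamps. State how much time one reading represents, so that numerator and denominator use the same rule. The measure is then bounded by 100%. Leave the overall closed loop percentage unchanged. If the measure is tabulated for the extension phase, as protocol 14.6 foresees, use the same definition.

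The cost is small: one SAP sentence, a merge of pump and CGM data that the trial already downloads, and a re-run of one descriptive table. SAP version 3.0 (May 2021) records that the initial analyses were complete, so the main-study change should be marked as a post-hoc correction. Protocol section 23 expected the extension to finish in October 2022, which left room to set the definition before its final tabulation. The reported percentage may become slightly lower; if no closed loop time falls outside CGM time, it will not change.

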
severity of hypoglycaemia, frequency of diabetic ketoacidosis (DKA) and nature and severity of other adverse events.
 
3. UTILITY: The objective is to determine the acceptability and duration of use of the closed loop system in this population.
 
4. HUMAN FACTORS: The objective is to assess emotional and behavioural characteristics of participants and parents/guardians and their response to the closed loop system and clinical trial using validated surveys (primary & extension phase), actigraphy and semi-structured qualitative interviews (primary phase only).
 
5. HEALTH ECONOMICS: The objective is to perform a cost utility analysis to inform reimbursement decision-making.
	
Study Design
 
The primary phase adopts an open-label, multi-centre, multi-national, randomised, two-period crossover study design contrasting closed loop glucose control and sensor augmented pump therapy in very young children with type 1 diabetes in the home setting. Two intervention periods will last 4 months each with 1 to 4 weeks washout period. The order of the two interventions will be random. The extension phase adopts a multi-centre, single arm design evaluating closed loop glucose control in very young children with type 1 diabetes in the home setting for 18 months from the end of the primary phase (UK sites only).

Study Endpoints
 
The primary endpoint: The primary endpoint is the between group difference in time spent with sensor glucose levels between 3.9 to 10.0 mmol/l (70 to 180 mg/dl) during the 4 months intervention period.
 
Other key endpoints*
 
 
• Time spent above target glucose (10.0 mmol/l) (180 mg/dl)
 
• HbA1c
 
• Average of glucose levels
 
• Time spent below target glucose (3.9 mmol/l) (70 mg/dl)
 
 
Secondary endpoints* include the following:
 
 
• Standard deviation, and coefficient of variation of glucose levels
 
	

- Time with glucose levels <3.0 mmol/l (54 mg/dl)
- Time with glucose levels in significant hyperglycaemia (glucose levels > 16.7 mmol/l) (300 mg/dl)
- AUC of glucose below 3.5 mmol/l (63 mg/dl)
- BMI SDS
- Total, basal, and bolus insulin dose

\* Endpoints regarding glucose levels will be based on sensor glucose data.

Extension Phase (UK sites only):

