## 10.5 Utility Evaluation

Utility evaluation is the frequency and duration of CGM use and use of the closed loop system at home.

- Percentage of time of closed loop operation
- Percentage of time of CGM availability

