129   Additionally, CGM metrics will be calculated every three months during the extension phase by  
130   inclusively pooling all CGM readings falling within each of the windows specified at each month  
131   in the table below:

Month	Window for Analysis
Month 3	Days 1-91
Month 6	Days 92-182
Month 9	Days 183-274
Month 12	Days 275-365
Month 15	Days 366-456
Month 18	Days 457-548

132

133   **4.2 Calculation of BMI SD Scores**

134   BMI standard deviation score will be calculated using the WHO growth chart.

135   **5. Analysis Datasets and Sensitivity Analyses**

136   **5.1 Analysis Cohorts**

- 137   • The primary analysis and all secondary analyses will be performed on a modified  
138   intention-to-treat basis with each day included in the treatment group assigned by  
139   randomization.
- 140   • A per-protocol analysis restricted to randomized participants with a minimum of 60% of  
141   available CGM readings during the control period and 60% CL system use during the CL  
142   period will be conducted for the primary outcome.
- 143   • Safety outcomes will be reported for all enrolled participants, regardless of whether the  
144   study was completed.

145 **6. Analysis of the Primary Efficacy Endpoint**

146 **6.1 Included Subjects**

147 In analyses conducted in the main study, only subjects with at least 168 hours of CGM data in at  
148 least one period will be included. If a subject has more than 168 hours of data in period 1 and  
149 then drops out of the study without any data in period 2, then he or she will be included in the  
150 analysis.

151 In the extension phase, analyses will include participants with at least 168 hours of CGM data  
152 during the SAP phase of the main study and at least 672 hours of CGM data during the extension  
153 phase. For the analyses conducted every three months during the extension phase, at least 168  
154 hours of CGM data will be required within a given three-month period to be included in the  
155 tabulations of summary statistics for that particular period.

156 **6.2 Missing Data**

157 Missing data will not be imputed for the primary analysis in this study.

158 **6.3 Statistical Methods**

159 Mean  $\pm$  SD or summary statistics appropriate to the distribution will be reported for the primary  
160 outcome and each of the key secondary outcomes listed below over the four month period by  

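### SAP 9.1 carries zero use to the end of the study, so a child who drops out during period 1 is scored 0% in a second-period arm that was never started

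*Combined protocol and SAP*

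**What the plan says.** Protocol 10.5 names two utility measures: closed loop use ("Percentage of time of closed loop operation") and CGM availability. The objective in the protocol synopsis reads "The objective is to determine the acceptability and duration of use of the closed loop system in this population".

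SAP 9.1 turns these into three percentages.
- **CGM use**, for both arms, divides "CGM readings by the expected number of readings during the four-month period".
- **Closed loop use**, in the closed loop arm only, is divided by the longest time for which the system could have been in use.
- **Closed loop use while using CGM** is operational time divided by the time CGM was available.

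Results are summary statistics by arm, with the range. SAP 9.1 and protocol 14.6 plan no test of use.

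The dropout rule in SAP 9.1 begins "If a subject drops out of the study in the middle of a period, then the subject will be counted as" and continues "not using the CGM or the closed loop system at all during the remainder of the study". It adds that these "time points will be counted as zero use in the calculation of CGM use and closed loop system" use. Protocol 14.6 has no dropout rule.

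**The concern.** The zeros run to the end of the study, not to the end of the period in which the child stopped. For a child who leaves in period 1, the remainder of the study contains the whole of period 2, which belongs to the other arm. Nothing in SAP 9.1 excludes an arm that was never begun.

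The by-arm figures would then include children who never received that arm's treatment. A family that left during pump therapy would count as a complete non-user of a closed loop system it was never given. A family that left during closed loop would count as having used no CGM in the control arm. At stake is how far the utility tables describe use of each treatment by those who started it.

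**Working it through.** **1. The texts side by side**
- SAP 9.1 reports use over the four-month period and refers back to an earlier definition. SAP 4.1 starts that period at the treatment initiation visit and ends it at 112 days or the end of treatment visit, whichever comes first. An arm with no initiation visit has no such period.
- The closed loop denominator is time for which the system could have been used. For a child never given the system, that is arguably nil.
- Closed loop use while using CGM becomes 0/0 for an unstarted closed loop arm. The SAP does not say what to do.
- The trigger is dropout in the middle of a period. A child who leaves the day before Visit 6 scores 0% in the second arm. A child who leaves in washout is not covered.
- For safety person-time, SAP 8.3 ends the period at the dropout date and charges nothing to a later period.

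**2. Inputs**

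The plan states no utility percentage to reproduce. Its sample size supplies the 72 and does reproduce:
- SD of the within-child difference = 10.3 × √(2 × (1 − 0.3)) = 12.19.
- Normal approximation: (12.19 × (1.960 + 1.282) / 5)² = 62.4, so 63. With the noncentral t, 64 gives 89.8% power and 65 gives 90.3%, so 65 is confirmed.
- 65 × 1.10 = 71.5, so 72. The allowance is 72 − 65 = 7 dropouts.

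Assumed, not in the documents: 90% or 95% use while in the study, all dropouts in period 1, and dropout halfway through the period (range: 10% to 90% of the way through).

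**3. Effect per child on the mean of the arm never started**

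Mean = u × (72 − k) / 72, where u is use in the others and k is the number of zero-scored children. Each child costs u/72:
- u = 90%: 1.25 points.
- u = 95%: 1.32 points.

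With u = 95%, k = 2 gives 92.4%, k = 4 gives 89.7% and k = 7 gives 85.8%. The reported minimum is 0% as soon as k = 1.

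**4. Both arms together (u = 90%, 7 dropouts, halfway through period 1)**

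A dropout contributes 45% to the arm that was started. The literal rule adds 0% in the other arm. The alternative leaves the unstarted arm out of the denominator.

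| Dropouts | Measure | Literal rule | Unstarted arm not scored |
|---|---|---|---|
| 7 closed-loop-first | CGM use, closed loop arm | (65×90 + 7×45)/72 = 85.6% | 85.6% |
| | CGM use, control arm | 65×90/72 = 81.25% | 65×90/65 = 90.0% |
| | Difference | +4.4 | −4.4 |
| 7 pump-first | Closed loop use, and CGM use in closed loop arm | 81.25% | 90.0% |
| | CGM use, control arm | 85.6% | 85.6% |
| 4 closed-loop-first, 3 pump-first | CGM use, closed loop arm | (65×90 + 4×45)/72 = 83.75% | 6030/69 = 87.4% |
| | CGM use, control arm | (65×90 + 3×45)/72 = 83.1% | 5985/68 = 88.0% |
| | Difference | +0.6 | −0.6 |

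Moving the dropout time from 10% to 90% of the period changes 85.6% to between 82.1% and 89.1%. In the one-sided case the shift in the between-arm difference is 90.0 − 81.25 = 8.75 points whatever the dropout time. In the near-balanced case it is about 1.2 points, although both levels fall by about 4 to 5 points.

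**The case against.** The wording may not be applied literally. The period definition in SAP 4.1 and the closed loop denominator both point to leaving out an unstarted arm, and a programmer might do so. That stands as evidence of a conflict within the SAP, but the dropout sentence itself says the opposite.

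Counting dropout as non-use in all randomised children is a recognised conservative convention with a known direction. The objective speaks of acceptability and duration of use in the population. It does not restrict itself to families once they have the system. This stands: the zero-filled figure is a legitimate summary and should not be discarded.

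Four stronger readings are tempting, and the documents do not support them.
- **That the by-arm CGM comparison is unreadable.** The tables are descriptive, a median moves little, and near-balanced dropout barely changes the difference.
- **That the rule contradicts the primary analysis.** SAP 6.1 keeps a child who "then drops out of the study without any data in period 2, then he or she will be included in the" analysis, and SAP 6.2 does not impute. But time in range cannot be computed without readings, while percentage use can be zero without them. The same child can have no glucose data and 0% CGM use.
- **That closed loop harms are routinely charged to the control arm.** Protocol 9.15 provides for efforts to keep children in follow-up after the intervention stops, so withdrawal for a closed loop event does not automatically trigger the rule. The carry-over also runs in both directions, and in the control arm it concerns CGM use only.
- **That mean closed loop use would fall to about 86%.** This puts all 7 allowed dropouts in one sequence and one period, about 7/36 = 19% of that sequence.

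SAP 9.2 requires flow charts of visits and dropouts. These would show who never started period 2, though no split by sequence is specified.

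**Conclusion.** The point holds as a fault in a descriptive table. Followed literally, SAP 9.1 puts 0% into an arm that a period 1 dropout never started, against the SAP's own period definition and denominator, and leaves the third measure undefined.

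Each such child lowers the arm mean by 1.25 to 1.32 points, given 72 randomised and 90-95% use in the others, and sets the minimum to 0%. The between-arm CGM difference moves materially only when period 1 dropout is unbalanced by sequence: 8.75 points in the most one-sided case and about 1.2 points with a 4-to-3 split. The use levels and dropout patterns are assumptions. The documents supply only the 72 and the 10% allowance.

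The primary endpoint and power are not affected. Zeros up to the end of the period in which the child stopped are defensible. The fault is only their extension into an arm not begun.

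**What to change.** In SAP 9.1, count zero use from the dropout date only to the planned end of the period in which the child stopped. Treat a period whose initiation visit (Visit 5 or Visit 7) did not take place as not started, and set all three measures to missing for it. This also settles the 0/0 case and dropout in washout. Give the number not started, by sequence, beside the table.

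The SAP revision history places version 3.0 after the initial analyses, so label the change as a post-hoc clarification. Show the pre-specified all-randomised, zero-filled figure next to the new one, not as an optional footnote.

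The cost is a short addition to the SAP text and one more tabulation. The arm denominators may differ by a few children, and reported use rises slightly. Because the change is post hoc and favours reported device use, both figures need to be visible.
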